20.5 MEASUREMENT OF INTRAOCULAR PRESSURE

Each time IOP is measured, the physician or technician should use a Goldmann tonometer. Take two measurements of IOP. If the measurements differ by more than 2 mmHg, take a third measurement. If two measurements are taken, record the mean on the case report form. If three measurements are taken, record the median on the case report form.

At all scheduled visits every attempt should be made to have these measurements taken at the same time interval to minimize the effect of daily fluctuations in pressure.

Guidelines for performing Goldmann tonometry are as follows:

1. The subject is told the purpose of the test and is reassured that the measurement is not painful. The subject is instructed to relax, maintain his or her position, and hold his or her eyes open widely.
2. One drop of a topical anesthetic, such as 0.5% proparacaine or 0.4% benoxinate, is placed in each eye, and the tip of a moistened fluorescein strip is touched to the tear layer on the inner surface of each lower lid. Alternatively, one drop of a combined anesthetic-fluorescein strip is touched to the tear layer on the inner surface of each lower lid. The tonometer and prism are set in correct position on the slit lamp.
3. The tension knob is set at 1 g. If the knob is set at 0, the prism head may vibrate when it touches the eye and damage the corneal epithelium. The 1 g position is used before each measurement. As a rule, it is more accurate to measure intraocular pressure by increasing rather than decreasing the force of applanation.
4. The 0 graduation mark of the prism is set at the white line on the prism holder. If the subject has more than 3 diopters of corneal astigmatism, the

area of contact between the cornea and the prism is elliptic rather than circular. In this situation the prism should be rotated to 45 degrees from the long axis of the ellipse—that is, the prism graduation corresponding to the least curved meridian of the cornea should be set at the red mark on the prism holder. An alternative approach is to average the intraocular pressure readings obtained with the axis of the prism horizontal and then vertical.

5. The cobalt filter is used with the slit beam opened maximally. The angle between the illumination and the microscope should be approximately 60°. The room illumination is reduced.
6. The subject is seated in a comfortable position on an adjustable stool or examining chair facing the slit lamp. The heights of the slit lamp, chair and chin rest are adjusted until the subject is comfortable and in the correct position for the measurement. The subject's chin is supported by the chin rest and the forehead by the forehead bar. The forehead bar should be well above the subject's eyebrows so the frontalis muscle can be used to open the eyes widely. The subject's collar and tie should be loosened if necessary. The subject should breathe normally during the test to avoid Valsalva's maneuver.
7. The palpebral fissure is a little wider if the subject looks up. However, the gaze should be no more than 15° above the horizontal to prevent an elevation of intraocular pressure that is especially marked in the presence of restrictive neuromuscular disease. A fixation light may be placed in front of the fellow eye. The subject should blink his eyes once or twice to spread the fluorescein-stained tear film over the cornea and then should keep his eyes open widely. In some subjects it is necessary for the examiner to hold the eyelids open with the thumb and forefinger of one hand. Care must be taken not to place any pressure on the globe because this raises intraocular pressure.
8. The operator sits opposite the subject in position to look through the microscope. The clinician moves the assembly toward the subject. When the black circle near the tip of the prism moves slightly, it indicates contact between the prism and the globe.
9. Alternatively, the assembly is advanced toward the subject until the limbal zone has bluish hue. The biprism should not touch the lids or lashes because this stimulates blinking and squeezing. Touching the lids also thickens the fluorescein rings, which may cause an overestimation of intraocular pressure.
10. The clinician observes the applanation through the biprism at low power. A monocular view is obtained of the central applanated zone and the surrounding fluorescein stained tear film. Using the control stick, the observer raises and lowers and centers of the assembly until two equal semicircles are seen in the center of the field of view. If the two semicircles are not equal in size, intraocular pressure is overestimated. The clinician turns the tension knob in both directions to ensure that the instrument is in good position. If the semicircles cannot be made "too small," the instrument

is too far forward. If the semicircles cannot be made "too large," the instrument is too far from the eye.

11. The fluorescein rings should be approximately 0.25 to 0.3 mm in thickness, that is, one tenth the diameter of the flattened area. If the rings are too narrow, the subject should blink two or three times to replenish the fluorescein; additional fluorescein may be added if necessary. If the fluorescein rings are too wide, the subject should dry his eyes lightly with a tissue, and the front surface of the prism should be dried with lint-free material. An excessively wide fluorescein ring is less of a problem than a very narrow ring but can cause the intraocular pressure to be overestimated.
12. The fluorescein rings normally undergo a rhythmic movement in response to the cardiac cycle. The tension knob is rotated until the inner borders of the fluorescein rings touch each other at the midpoint of their pulsations. The intraocular pressure is the mean of these 2 readings.
13. Intraocular pressure is measured in the study eye twice. If the 2 readings differ by 2 mmHg or less the average is the IOP. If the 2 readings differ by > 2 mm Hg, a third reading is taken.
14. The reading obtained in grams is multiplied by 10 to give the intraocular pressure in millimeters of mercury. This value is recorded along with the date, time of day, list of ocular medications, and time of last instillation of ocular medication if IOP is measured on different days, an attempt should be made to standardize the time.

Errors in measurement can arise from a number of factors, including the following:

1. Inadequate fluorescein staining of the tear film causes an underestimation of intraocular pressure.
2. Elevating the eyes more than 15° above the horizontal causes an overestimation of intraocular pressure. Widening the lid fissure excessively causes an overestimation of intraocular pressure.
3. Repeated tonometry reduces intraocular pressure, causing an underestimation of the true level. This effect is greatest between the first and second readings, but the trend continues through a number of repetitions.
4. A scarred, irregular cornea distorts the fluorescein rings and makes it difficult to estimate intraocular pressure.
5. The thickness of the cornea affects intraocular pressure readings. If the cornea is thick because of edema, intraocular pressure is underestimated. If the cornea is thick because of additional tissue, intraocular pressure is overestimated. The Goldmann tonometer is accurate after epikeratophakia.
6. If the examiner presses on the globe or if the subject squeezes his eyelids, intraocular pressure is overestimated.

7. If corneal astigmatism is greater than 3 diopters, intraocular pressure is underestimated for with the rule astigmatism and overestimated for against the rule astigmatism. The intraocular pressure reading is inaccurate 1 mm Hg for every 3 diopters of astigmatism.

Calibration and Documentation

The calibration of the tonometer will be checked at least once every three months with the weight system at 0, 2, and 6 grams as supplied by the manufacturer. When the calibration steps provide readings within ± 2 mmHg of the target value for each weight, the tonometer is considered adequately calibrated. However, if the variation exceeds this amount, a different adequately calibrated instrument should be used for IOP measurements.

The investigator must maintain written documentation in a log (hardcopy or electronic format acceptable) of the calibration of each tonometer used at the beginning and throughout the study period, and make these records available to study monitors for review. Documentation must describe the unit (by model and serial number or other permanent identifier), the date of each calibration, the name or initials of the person performing the calibration, and an indication as to whether or not the unit passed the calibration. If not calibrated successfully, a note should be entered in the log about contacting the authorized manufacturer's representative for repair and what repairs were required. Following any repair, another calibration should be documented prior to clinical use.

Diurnal IOP

In order to determine the mean diurnal intraocular pressure (IOP) measurements at baseline and 12 months, IOP measurements should be taken at 9:00AM ± 1.5 hours, 12:00PM ± 1 hour, and 4:00PM ± 2 hours. The three IOP measurements should then be averaged to determine the mean diurnal IOP.

20.6 VISUAL FIELD EXAMINATION

Visual fields must be automated threshold visual fields, 24-2 Humphrey Stimulus III. The SITA Standard must be used for the visual field conducted at the pre-operative evaluation and all subsequent evaluations. Visual fields must be reliable at screening for eligibility, defined as less than 33% false positives, false negatives, and fixation losses. A visual field done within 90 days prior to the subject informed consent date and in accordance with the 24-2 SITA Standard requirements can be used for the baseline evaluation. For visual fields that do not meet the reliability standards, the test should be repeated within two weeks.

Visual fields are to be performed with a non-dilated pupil unless, in the opinion of the investigator, the pupil is so miotic that dilation is required (e.g., < 3mm). If dilation was performed at screening, it should be performed at all subsequent visual field

examinations. However, dilation should not be performed before the IOP measurement on the appropriate visits.

It is recommended that the following set up occur for the visual field:

SITA Standard 24-2 test

- using the white, size III stimulus,
- Foveal Threshold ON,
- Head Tracking ON and
- Vertex Monitoring OFF.

The appropriate trial lens as defined by the perimeter should be used.

20.7 DILATED FUNDUS EXAMINATION

A mydriatic should be used to dilate the pupil so that an examination of the fundus can be conducted with an indirect ophthalmoscope and slit lamp biomicroscopy (with contact lens, Hruby lens or 60-, 66-, 78-, or 90 diopter lens). The appearance of the optic disc, macula, vessels and periphery should be evaluated and reported on the Baseline form. A measurement of the cup to disc ratio should be made and reported.

20.8 SLIT LAMP EXAMINATION

The clinician will examine the conjunctiva, cornea, anterior chamber, lens and anterior vitreous of the eye with the aid of a slit lamp, which is a table-mounted binocular microscope. Fluorescein dye will be instilled into the ocular cul-de-sac to facilitate this examination. In addition to the following, any evidence of pigment dispersion visible in slit lamp examination should be evaluated and noted.

Iris

Findings of Atrophy/Erosion; Peaking; and Rubeosis should be noted. Each will be evaluated using a scale of None (0), Mild (+1), Moderate (+2) and Severe (+3).

Cornea - Edema

None (0)	Transparent and clear or less than mild
Mild (+1)	Dull glassy appearance
Moderate (+2)	Dull glassy appearance of epithelium with large number of vacuoles
Severe (+3)	Epithelial bullae and/or stromal edema, localized or diffuse, with or without stromal striae

Cornea - Staining/Erosion

None (0)	No fluorescein staining of epithelium, OR less than mild
Mild (+1)	Slight fluorescein staining confined to a small focus
Moderate (+2)	Regionally dense fluorescein staining (1 mm or greater in diameter) with underlying structure moderately visible
Severe (+3)	Marked fluorescein staining or epithelial loss

Anterior Chamber

The following system is recommended for grading of aqueous cells and flare using a slit beam 1.0 mm wide and 1.0 mm long.

Cells

[figure not shown]
0 = < 1 cell seen
0.5+ = 1-5 cells seen
1+ = 6-15 cells seen
2+ = 16-25 cells seen
3+ = 26-50 cells seen
4+ = > 50 cells seen

Flare

0 = None
1+ = Faint
2+ = Moderate (iris and lens details clear)
3+ = Marked (iris and lens details hazy)
4+ = Intense (fibrin or plastic aqueous)

[figure not shown]
The presence of hypopyon is recorded separately. The presence of "microhyphema" or "layered hyphema" in the anterior chamber should also be recorded. Layered hyphema will be graded using the following scale (If Grade 1, also record size in mm on the CRF).³⁵

³⁵ <http://www.aao.org/image/hyphema-grading-system-2>

Posterior Capsule Opacification

As a routine part of the slit lamp examination, posterior capsule opacification (PCO) will be evaluated using the following scale:

Other Slit Lamp Findings (complete for each finding)

- Trace
- Mild
- Moderate
- Severe

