9 STUDY PROCEDURES

9.1 STUDY SCHEDULE

Table 1: Study Visit Schedule

Note: The fellow eye should be followed per the PI's usual practice based on the ocular health of the fellow eye.

PROCEDURE	SCREENING (DAY -45 TO -6)	BASELINE (DAY -7 TO 0)	SURGERY (DAY 0)	1 DAY (DAY 1)	1 Wk (DAY 5-9)	1 M (DAY 21-35)	3 M (DAY 70-98)	6 M (DAY 150-210)	12 M (DAY 330-420)	12 M WASHOUT ²⁹ (DAY 330-420)
Informed Consent	X									
Demographics	X									
Medical & Ocular History	X	X								
Medication Log	X	X	X	X	X	X	X	X	X	X
BCVA (ETDRS), with manifest refraction	X	X			X	X	X	X	X	
Visual Field (Humphrey 24-2 SITA)	X									X
IOP (Goldmann)	X			X	X	X	X	X	X ³⁰	
Unmedicated diurnal IOP (Goldmann)		X							X ³¹	X
Slit Lamp Exam	X	X		X	X	X	X	X	X	
Gonioscopy	X				X	X	X	X	X	
Dilated Fundus Exam/C:D Ratio	X								X	
Eligibility Assessment	X	X								
Cataract Extraction + ab-interno transluminal viscoelastic delivery and trabeculotomy			X							
AE Assessment	X	X	X	X	X	X	X	X	X	X

²⁹ The 12 month washout visit is only required for subjects who are taking hypotensive medications at the 12 month visit.

³⁰ This is only required for subjects who are taking hypotensive medications at the 12 month visit.

³¹ If subject is not on any hypotensive medications, a diurnal IOP measurement should be obtained at the 12 month visit as unmedicated IOP.

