9.11 SUBJECTS LOST TO FOLLOW-UP

Subjects who do not show up for a follow-up must be contacted to attempt to have them come for the follow-up. For those subjects who cannot be reached, at least 3 phone call attempts should be made and documented. If still no response, a registered letter shall be sent to the address on file for the subject in an attempt to make contact. If a subject misses two consecutive follow-up visits without any contact with the study staff, the subject will be considered lost-to-follow-up unless there is a further communication by the subject.

10 ADVERSE EVENTS (AEs)

Adverse Events are defined below. Adverse events that occur in the eye during the trial, whether they are considered to be device related or not, must be documented in the subject's records. Date of the event, its severity, treatment (if any) and the assessed relationship of the event to the study device will be recorded on the Adverse Event Form. Conditions which exist at the time the subject is enrolled do not need to be recorded as adverse events unless they increase in severity during the study.

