10.2 LIST OF ANTICIPATED POTENTIAL ADVERSE EVENTS

Anticipated potential adverse events listed below include those that might reasonably be expected to occur in this study because they are associated with glaucoma, cataract surgery, ab-interno transluminal viscoelastic delivery, trabeculotomy, and/or the risk analysis for OMNI System. Adverse events may occur intra-operatively or post-operatively.

- Layered Hyphema $\geq 1\text{mm}$ (Microhyphema or Hyphema $<1\text{mm}$ is expected and will not be considered an AE)
- IOP increase $\geq 10\text{ mmHg}$ above baseline IOP at ≥ 1 month visit³³
- IOP increase requiring management with systemic medication at ≥ 1 month visit³²
- Need for secondary surgical intervention to manage IOP³²
- Hypotony (IOP $<6\text{ mmHg}$)³⁴ with at least one of the following conditions:
 - Flat anterior chamber requiring anterior chamber reformation
 - Corneal folds
 - Choroidal effusions requiring or undergoing surgical drainage
 - Suprachoroidal hemorrhage

³³ To avoid double counting an event, events of IOP $\geq 10\text{ mmHg}$ above baseline IOP at ≥ 1 month visit that require management with systemic medication or secondary surgical intervention should be reported as “IOP increase requiring management with systemic medication at ≥ 1 month visit” or “Need for secondary surgery intervention to manage IOP,” respectively.

³⁴ Hypotony is defined as “early” if it occurs within 2 weeks of surgery and “late” if it occurs more than 2 weeks after surgery

e) Maculopathy

- Corneal injury
- Corneal edema after 1 week
- Corneal abrasion
- BCVA loss of ≥ 10 letters (ETDRS) at or after 3 months postoperative
- Descemet's membrane tear or detachment
- Chronic anterior uveitis (inflammation of grade 1+ or worse persisting for more than 3 months post-operatively or that recurs less than three months after discontinuing treatment)
- Wound leak
- IOL dislocation and/or damage
- Intracorneal Hematoma
- Posterior capsular tear
- Pupillary block
- Cyclodialysis
- Iridodialysis or significant iris damage
- Peripheral Anterior Synechiae > 1 clock hour
- Suture abscess or other local infection
- Flat or shallow anterior chamber requiring anterior chamber reformation
- Aqueous misdirection
- Choroidal detachment
- Choroidal effusion requiring surgical drainage
- Choroidal hemorrhage
- Suprachoroidal hemorrhage
- Vitreous hemorrhage
- Perforation of sclera
- Clinically significant cystoid macular edema
- Retinal detachment
- Retinal tear

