11.5.3 OTHER SAFETY OUTCOMES

The number and percent of eyes reported with each kind of slit lamp findings, gonioscopy findings, and dilated fundus examination findings at each visit will be provided.

The descriptive statistics for the continuous variables will be derived for the visual field mean deviation (MD) and pattern standard deviation (PSD).

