20.9 GONIOSCOPY

Gonioscopy will be conducted as part of the screening process to verify that the subject has an open angle and to identify any anterior synechiae as well as determine if there is any pigment dispersion. A Zeiss, Sussman or similar lens should be used and gonioscopy conducted in a dark room with a narrow, short slit beam that does not pass through the pupil and without a fixation light being used. The Shaffer method will be used as follows: grade 4, wide open (35°-45°); grade 3, moderately open (25°-34°); grade 2, moderately narrow (20°); grade 1, very narrow (10°); grade 0, closed (0°). The grade number will be reported for each quadrant of the eye in the appropriate location on the form.

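### The slit-lamp safety table (11.5.3) counts eyes with a finding visit by visit and never compares an eye with its own Baseline, so new or worsened findings can go unseen in that table

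*Combined protocol and SAP*

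**What the plan says.** **Grading.** Section 20.8 grades iris signs on a four-level scale: "Each will be evaluated using a scale of None (0), Mild (+1), Moderate (+2) and Severe (+3"). Corneal edema and corneal staining also run from 0 to +3. For the anterior chamber, "The following system is recommended for grading of aqueous cells and flare", with levels up to 4+ and an extra 0.5+ level for cells. Other findings run from trace to severe. Layered hyphema and posterior capsule opacification have scales too, shown as figures. Not every sign is graded: "The presence of hypopyon is recorded separately", and pigment dispersion is simply noted.

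**Schedule.** The "Slit Lamp Exam" row of Table 1 (Section 9.1) is marked at Screening, Baseline, Day 1, Week 1 and Months 1, 3, 6 and 12. It is not marked at surgery or at the 12-month washout visit. Gonioscopy is marked at Screening and at five postoperative visits. Section 20.9 says of it: "The grade number will be reported for each quadrant of the eye".

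**Analysis.** Section 11.5.3 plans this for all three exams: "The number and percent of eyes reported with each kind of slit lamp findings, gonioscopy findings, and dilated fundus examination findings at each visit". It mentions no grade, change from Baseline, shift table or worst postoperative grade. Section 11.5 sets the population as ITT with all available data.

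**Adverse events.** Section 10 exempts conditions present at enrollment from recording "unless they increase in severity during the study". Section 11.5.1 counts eyes with at least one event of each type and tabulates events by the highest severity per eye.

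**The concern.** The study has a single arm, so the only internal reference for an exam finding is the same eye before surgery. A count of affected eyes at a visit is a marginal prevalence. It does not say whether an affected eye was already affected, became affected after surgery, or got worse. A flat percentage across visits could then be read as absence of harm when some eyes had deteriorated and others had cleared.

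The plan does use within-eye change for another safety measure: Section 11.5.2 sorts eyes by letters of BCVA gained or lost at each postoperative visit. The graded exam signs get no equivalent, although the grades are collected at Baseline and repeatedly afterwards.

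**Working it through.** The plan states no figure for this table, so there is nothing to reproduce. The check is whether the planned count can stay constant while eyes worsen. N = 145 is the planned number of treated subjects (synopsis; Section 9.2). **All other counts below are assumed for illustration and are not in the documents.**

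**1. Presence count by visit.** Suppose 20 eyes have a mild finding at Baseline and 125 have none. Later 6 of the 20 resolve, 8 of the 20 go from mild to severe, 6 stay mild, and 6 of the 125 develop a moderate finding.

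| Grade | Baseline | Later visit |
|---|---|---|
| None | 125 | 125 − 6 + 6 = 125 |
| Mild | 20 | 20 − 6 − 8 = 6 |
| Moderate | 0 | 6 |
| Severe | 0 | 8 |
| Any finding | 20 | 6 + 6 + 8 = 20 |

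- Presence count: 20/145 = 13.8% at both visits.
- Eyes worse than at Baseline: 6 + 8 = 14, and 14/145 = 9.7% (exact Clopper-Pearson 95% CI 5.4% to 15.7%). All 14 moved by at least two grades, 8 of them to severe.

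**2. The same data by grade.** If 'kind' of finding is read to include grade, the table shows 6 moderate and 8 severe eyes where there were none, so the worsening becomes visible. The table still cannot say how many eyes are newly affected:

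- No new case: 14 of the 20 mild eyes worsen and 6 stay mild.
- 20 new cases: all 20 mild eyes resolve and 20 other eyes become 6 mild, 6 moderate and 8 severe.

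Both give the same column totals, so anything from 0/145 to 20/145 (0% to 13.8%) newly affected eyes fits.

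**3. Pure offsetting.** Suppose 29/145 = 20.0% are affected at Baseline, 10 resolve, and 10 other eyes become affected at the same grades. The later count is 29 − 10 + 10 = 29, again 20.0%, and a by-grade display is unchanged too. A shift table shows 10/145 = 6.9% newly affected (exact 95% CI 3.4% to 12.3%).

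**4. Does the adverse event route fill the gap?** In part.

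- Worsening of a pre-existing condition is recordable under Section 10. Section 11.5.1 then counts it per eye, and resolution in other eyes cannot cancel it.
- No text says which change of slit-lamp grade amounts to an increase in severity, and the adverse event severity level is not defined by the slit-lamp grade.
- Several entries in 10.2 carry thresholds: corneal edema counts after 1 week, and chronic anterior uveitis needs grade 1+ or worse for more than 3 months or recurrence within three months of stopping treatment. For changes below such thresholds, the systematic record is the exam data.

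**5. Later visits.** Under Section 9.9, subjects who need another IOP-lowering procedure are followed for a time and then withdrawn. They leave the later per-visit counts, whereas a worst-grade table keeps the grades recorded before they left.

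**The case against.** **The safety analysis as a whole does capture worsening.** A reader might infer from 11.5.3 that a move from mild to severe is lost everywhere. The documents do not support that. Sections 10 and 11.5.1 provide a cumulative per-eye count and a maximum-severity table, and 10.2 lists many events visible at the slit lamp, such as layered hyphema of at least 1 mm and significant iris damage. This objection stands and confines the point to the 11.5.3 tables. What remains is that the adverse event route depends on investigator reporting.

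**The table may already be by grade.** The wording leaves this open, and for gonioscopy the grade is itself the recorded result. On that reading a rise in grade shows in the totals. Steps 2 and 3 show that within-eye change and offsetting stay hidden.

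**Offsetting is unlikely for several signs.** The exclusions remove uveitic and neovascular glaucoma and give corneal edema and Fuchs' dystrophy as examples of disqualifying pathology. Posterior capsule opacification cannot precede the study eye's cataract extraction. For signs that are rare at Baseline, the postoperative count is close to the number of new cases. This stands. Offsetting is plausible mainly for signs such as corneal staining or iris atrophy, and the documents give no prevalence for either.

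**Synechiae.** Because 10.2 lists "Peripheral Anterior Synechiae > 1 clock hour" while 20.9 specifies only a quadrant grade, a reader might infer that synechial extent is not recorded. Section 20.9 also says that gonioscopy is to identify anterior synechiae, and the case report forms are not in the documents. That inference cannot be drawn, and no change to the listed event is called for.

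**Conclusion.** The point holds for the exam tables of 11.5.3. As written, they give marginal prevalence by visit with no within-eye comparison, so they cannot separate pre-existing from new findings. Unless they are split by grade, they also cannot show a worsening grade. The adverse event tables cover part of this, subject to what the investigator reports.

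The documents cannot show how large the effect would be. The 9.7% and 6.9% above rest on assumed counts and show only that masking is possible, not that it is likely. For signs that are rare before surgery the loss is small.

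This is a minor improvement to descriptive safety reporting. It does not affect any endpoint test, the significance level or the sample size.

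**What to change.** In Section 11.5.3:

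- Keep the per-visit summaries at every scheduled visit, including Day 1 and Week 1, and state that graded signs are presented by grade.
- For each graded slit-lamp sign, add on the ITT population a shift table from the Baseline grade to the worst postoperative grade, with early visits (Day 1 and Week 1) shown separately from 1 month onward. Add a second shift table from Baseline to the 12-month grade.
- With each shift table, give the number and percent of eyes, with exact 95% CI, that have a new finding or a higher grade category than at Baseline. Defining worsening by category deals with the 0.5+ level for cells.
- Present the Shaffer grades from gonioscopy in the same way, with Screening as the reference because gonioscopy is not scheduled at Baseline. Lower Shaffer grades mean a narrower angle, so state the direction that counts as worse.

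Shift tables should add to the per-visit counts, not replace them. A table limited to 1 month onward would drop the early postoperative findings.

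The cost is a few lines of SAP text and some extra descriptive tables from grades already collected. No visit, subject or case report form item is added.
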